19.0 Appendices	
Appendix A – Usability Testing Measures (Aim 1)	
Appendix B – Patient Assessments (Aims 2 and 3)	
Appendix C – Healthcare Professional Assessments (Aim 2)	
Appendix D – Informed Consent Documents	

1.0 SCHEMA

In 2010, cancers of the oral cavity, pharynx, and larynx (which comprise head and neck squamous cell carcinoma [HNSCC]) were estimated to account for 49,260 new cancer cases in the United States[1]. In addition, approximately \$3.2 billion[2] is spent in the U.S. each year on treatment of HNSCCs. Treatment for HNSCC includes surgery or radiation therapy and can lead to considerable functional impairment, potential disfigurement, and emotional distress. As a consequence, HNSCC patients experience significant decrements in quality of life (QOL), poorer interpersonal relations, and increased social isolation[3]. Studies suggest that psychoeducational interventions can improve quality of life, reduce psychological distress, and enhance coping with cancer in various cancer populations[4-5]. However, few such programs have been developed for HNSCC patients. This empirical gap is surprising given that studies have noted that HNSCC patients have considerable informational needs that are not being adequately addressed[6]. In addition, due to the potential effects of cancer and cancer treatment on facial appearance and speaking ability, psychosocial interventions that are delivered in-person may be less appealing to some HNSCC patients who are reluctant or unwilling to engage in social interactions due to social anxiety or feeling stigmatized[7-9]. In addition, patients often find themselves having to manage extensive treatment and rehabilitation appointments, and therefore, they have little additional time to participate in or take advantage of any available psychosocial services. Indeed, previous studies have reported low attendance to be a common barrier to delivering interventions for HNSCC patients[10-11], and patients have also reported psychosocial services to be inaccessible to them[12]. Thus, the development of a widely accessible program that provides didactic information on treatment-related side effects, as well as cognitive and behavioral strategies to enhance psychosocial adjustment and QOL following treatment, would address this gap. In consideration of these factors, web-based interventions represent one option for delivering key information to this population in an efficacious, practical and acceptable format. If effective, this medium also has high dissemination potential.

Thus, the overall goal of the proposed project is to develop and examine the acceptability of a theory-guided, web-based multimedia intervention program for HNSCC patients who have recently completed radiation therapy. Our long-term goal is to evaluate the effects of such an intervention on QOL among HNSCC patients. As a first step, we propose to create appropriate content, including informational text, brief video scripts, and animated graphics. Next, we will develop a test website that includes prototypes for four components of the proposed web-based program. The specific aims of the proposed project are to:

Aim 1: Develop a prototype web-based multimedia program that includes four components (or topic areas), including: 1) Head and Neck Cancer and its Treatment; 2) Changes in Swallowing and Oral Care; 3) Changes in Speech; and 4) Coping with Cancer. During the first 7 months, we will create the content and develop a prototype web-based program that presents both didactic information and cognitive and behavioral strategies for coping with treatment of HNSCC. Usability testing will be conducted with 5 HNSCC patients. Revisions based on patient feedback will be incorporated.

Aim 2: Evaluate acceptability and satisfaction with the prototype web-based program in a sample of up to 75 HNSCC patients and 5 expert professionals. The web-based program developed in Aim 1 will be evaluated by up to 75 patients who are currently undergoing or have recently completed radiation therapy and 5 healthcare professionals who work with HNSCC patients. Satisfaction and acceptability will be demonstrated if mean ratings meet specified criteria (see **Section 12.2.b. Indicators of Success**).

Exploratory Aim 3: Obtain preliminary data on potential program impact in a sample of up to 75 HNSCC patients. Measures of psychosocial functioning and self-efficacy will be assessed at pre- and post-program assessment, in order to obtain preliminary data on potential intervention impact. These data will be used to calculate potential effect sizes and support a future large-scale, randomized trial to evaluate the effectiveness of the web-based program in enhancing QOL among HNSCC patients.

2.0 INTRODUCTION

2.1. Background

2.1.a. Quality of Life Following Treatment. Despite advances in diagnostic tools and treatment modalities, treatment for HNSCC often confers considerable functional impairment. Consequently, HNSCC patients must cope not only with the diagnosis of cancer, but also with the physical sequelae of treatment. Treatment can result in: changes in swallowing, speech, and social functioning; dry mouth; need for nutritional supplements; pain; difficulties in social eating; and impaired sexual functioning[14]. Routine daily activities can become extremely challenging as patients may experience speech difficulties or impaired eating ability (e.g., difficulty swallowing, problems with drooling and chewing food)[15-17]. Many patients report both physical and psychosocial complaints even after successful therapy[18], and long-term deficits in QOL have been reported up to 10 years post-treatment[19].

Given the broad-ranging effects of treatment, it is surprising that 73% of HNSCC patients reported receiving little or no information during or following the treatment period[20]. A perceived lack of information has been associated with posttreatment uncertainty, anxiety and depression[21]. In contrast, HNSCC patients who received more information about the disease and the treatment experience reported fewer psychosocial problems[21]. Because the perception of having obtained adequate information is an important predictor of positive rehabilitation outcomes in the 2- to 6-year posttreatment period[20], there is a clear need for HNSCC patients to be able to obtain information about their disease and post-discharge care[22] in an accessible format.

2.1.b. Interventions can Lead to Enhanced Quality of Life. Psychosocial interventions can significantly enhance psychosocial functioning in cancer patient populations[4-5]. Although many programs have been developed for cancer patients (notably, breast cancer patients[23-24]), few have been developed for HNSCC patients. The few interventions tested have generally yielded beneficial effects among HNSCC patients[25-26], particularly when they are provided immediately following treatment. However, barriers to participation have also been noted. Specifically, requiring HNSCC patients to attend **in-person** sessions is a major barrier to participation, and compliance with interventions that entail multiple in-person interactions is difficult to achieve[27]. Hence, web-based programs, which do not require an in-person session, may greatly reduce or eliminate such barriers. Greater confidence in the effectiveness of a web-based program is also derived from a study that compared different approaches for delivering a coping strategies intervention for HNSCC patients (in-person with a therapist vs. a self-contained workbook with no therapist sessions)[28]. In both formats, the intervention was comprised of a workbook that covered various topics on coping skills, effective use of social support, problem-solving techniques, goal setting, and relaxation training[29]. Overall, all patients receiving the intervention program (regardless of format) reported improved QOL compared to control group patients receiving usual care[28, 30]. Further, the home format was as effective in enhancing QOL as the therapist-delivered format, thereby suggesting that such programs can be appropriately adapted for web-based delivery. In sum, a web-based program would be responsive to patient preferences for the receipt of materials and interventions that can be viewed at home, as well as reduce barriers to participation in such programs. In turn, such programs may yield positive effects on QOL and psychological adjustment among HNSCC patients[26, 30-31].

Rationale for a web-based intervention. Web-based psychoeducational interventions are increasingly common[32-36], but not within the HNSCC context. A web-based approach for this underserved population has several practical advantages: **First**, empirical evidence (and our pilot data, see Section 2.1.d.) suggests that patients prefer to receive materials that they can view at home[30]. There is often insufficient time for patients to absorb critical information during medical appointments[13] and it is difficult to retain such information under stress. **Second**, for patients who are reluctant to engage in social interactions following treatment[7-9], web-based content offers an interim approach for providing strategies to facilitate re-entry into social interactions when ready. Learning about and practicing strategies within

one's home and watching videos of how other HNSCC survivors have overcome concerns related to social engagement may increase confidence in re-initiating social interactions. **Third**, the Internet offers a functional advantage over print materials, particularly through the transmission of video. Videotaped vignettes can increase knowledge about cancer and treatments[37-38] and video modeling can improve patient self-care practices[39]. Web-based programs have yielded benefits ranging from decreases in pain to improved QOL[40-41]. **Fourth**, a web-based approach has high dissemination potential to the larger population of HNSCC patients. Over 73% of the US population reports Internet use[42]. Among home Internet users, almost 80% have high-speed Internet access allowing users to watch or download video online[43]. In sum, given the trend of increasing Internet use, it has become an essential tool for disseminating important health information[44-46].

2.1.c. A Theoretical Framework to Guide Intervention Development. Social Cognitive Theory (SCT)[60-64] has been widely used to guide health promotion interventions, and it proposes that behaviors are learned through information provision and vicarious process. Guided by SCT, interventions can teach skills through demonstration and physical rehearsal (e.g., exercises to increase active range of motion; oral care), which results in positive self-efficacy and outcome expectancies. A recent SCT-based intervention demonstrated that behavioral modeling was effective in promoting physical rehabilitation and reducing functional limitations in the injury recovery setting[65]. Patients who received the modeling intervention reported greater self-efficacy as well as greater objective functional outcome scores compared to controls[65]. Thus, the proposed program will attend to self-efficacy expectations of patients by providing them with various exercises to enhance coping and improve functional abilities (e.g., demonstrating exercise movements, teaching coping skills, modeling strategies for improving communication, providing tips for enlisting support from family and/or friends) and will include personal experiences of other survivors.

2.1.d. Preliminary Studies. With support from the Keystone Program in Head and Neck Cancer, the research team has been conducting work directly relevant to this proposal:

i) Psychosocial Functioning and Informational Needs in HNSCC Patients. The research team conducted a pilot study of HNSCC patients (n = 88)[52]. Participants were predominantly male (67.8%) with a mean age of 58.9 years (SD = 10.8). Over half (58%) was classified as having early-stage disease. Participants reported high levels of cancer-specific distress (M = 18.17, SD = 10.32) as measured by the Impact of Events Scale (IES[53]). Patients also reported high levels of general distress (M = 30.61, SD = 23.26) on the combined subscales of anxiety, depression, and anger from the Profile of Mood States (POMS[54]). Our findings are consistent with previous studies demonstrating significant levels of psychological distress among HNSCC patients[3, 17, 55] and support the need for developing psychosocial intervention programs for this population[13, 50]. Patients were queried about: 1) their levels of interest in receiving additional programs; 2) the type of program they desired; and 3) their preferred method for receiving such programs. All participants indicated that they would like to receive additional programming, particularly focused on treatment side effects. When asked about their preferences and needs, 89.7% of patients reported that they preferred to receive additional information they could read or view at home. The majority (79.3%) reported that they have a computer at home and 88% reported having Internet access (either at home or work). The majority of patients preferred to receive information either during treatment or shortly after treatment. The most requested topics included: 1) Basic information about HNSCC and treatment; 2) Information about changes in swallowing and speaking following treatment; 3) Tips and strategies to help make eating and speaking easier; 4) Tips for coping with stress and anxiety; 5) How to stay healthy after treatment.

ii) Psychosocial Interventions for Cancer Patients and At-Risk Populations. The research team will work closely with Triad Interactive to develop the proposed web-based intervention. Triad Interactive has extensive experience in developing multimedia interventions in the oncology setting. For example, Triad Interactive designed and developed an interactive multimedia intervention (delivered via CD-ROM) to enhance knowledge about Microsatellite Instability (MSI) Testing and decision-making about MSI testing.

The total development time of the CD-ROM, including modifications, was 6 months. Results were uniformly positive, with 92.5% of CD-ROM participants reporting that the educational information was presented clearly, and 87.6% reported that they learned new information. Although the program was delivered via CD-ROM, it was developed using Web-ready technologies including HTML, JavaScript, and Adobe® Flash®. Triad Interactive has also been involved in the graphic and instructional design, production, and programming for other NCI-funded studies including an interactive web-based program to facilitate decision making about prostate cancer screening (Lombardi Cancer Center); and an interactive computer-based program for decision making about *BRCA1/2* genetic testing (Mt. Sinai School of Medicine).

In sum, the preliminary findings suggest the following: 1) HNSCC patients report poor QOL and elevated distress, which supports the need for developing accessible intervention programs for this population; 2) most HNSCC patients (90%) noted that they would prefer to have informational materials that they could view at home, particularly on topics related to: cancer and cancer treatment; changes in speech and swallowing following treatment; and coping skills and communication training; and 3) the development of the proposed multimedia intervention is feasible to accomplish within the grant funding period. Finally, our team offers a diversity of expertise, including expertise in psycho-oncology and intervention development ([name], [name]), head and neck oncology (with Drs. [name], [name], and [name] representing surgical, medical, and radiation oncology, respectively), biostatistics ([name]), pain management ([name]), physical rehabilitation ([name]), and speech pathology ([name]).

Data obtained from this project will be used to further refine the web-based program and submitted as preliminary data in support of a randomized trial to evaluate the effectiveness of the web-based program in enhancing QOL among HNSCC patients. In that future study, it is hypothesized that use of the web-based program will contribute to enhanced patient QOL and psychosocial adjustment compared to a control group.

2.2. Rationale

Head and neck cancer and its subsequent treatment-related effects can have a significant negative impact on QOL, psychosocial adjustment, and interpersonal relations[3]. Psychoeducational interventions can be effective in improving QOL[4-5]; however, few programs have been developed for HNSCC patients despite preliminary data indicating a need for such programs in this patient population. The proposed project will be one of the first to develop a web-based intervention for HNSCC patients. At present, there are no similar existing programs for HNSCC patients despite the fact that such programs have yielded benefits for other cancer patient populations (e.g., breast, prostate). As such, building a theory-based resource for this patient population, and using the Internet to deliver such a resource, represents an innovative approach that may have a significant impact on QOL and psychological adjustment among a survivor population that experiences considerable morbidity.

3.0 OBJECTIVES

The objectives of the proposed study are to:

Aim 1. Develop a prototype web-based multimedia program that addresses four components, including: 1) Head and Neck Cancer and its Treatment; 2) Changes in Swallowing and Oral Care; 3) Changes in Speech; and 4) Coping with Cancer. We will create the content and develop a prototype web-based program that presents both didactic information and cognitive and behavioral strategies for coping with treatment of HNSCC. Material presented in the web-based program will include informational text, brief videos, and graphics and animation.

Aim 2. Evaluate acceptability and satisfaction with the prototype web-based program in a sample of up to 75 HNSCC patients and 5 expert professionals. Specifically, the prototype developed in Aim 1 will be

evaluated by up to 75 patients who are currently undergoing or have recently completed radiation therapy and 5 healthcare professionals who work with the HNSCC patient population.

Exploratory Aim 3. Obtain preliminary data on potential program impact in a sample of up to 75 HNSCC patients. Measures of psychosocial functioning and self-efficacy will be assessed at pre- and post-program assessment, in order to obtain preliminary data on potential intervention impact. These data will be used to calculate potential effect sizes and support a future large-scale, randomized trial to evaluate the effectiveness of the web-based program in enhancing QOL among HNSCC patients.

3.1 What are the dependent variables? Aim 1 is the development of the web-based program. For Aim 2, the primary dependent variables include satisfaction and acceptability of the web-based program among HNSCC patients and healthcare professionals. For Aim 3, exploratory dependent variables include psychosocial functioning and self-efficacy.

3.2 What are the independent variables? Independent variables include demographic variables (e.g., age, gender, education level, race/ethnicity, income, area of residence); medical and disease-related factors (e.g., tumor site, stage, grade of differentiation, and performance status); treatment-related variables (e.g., time since treatment), and prior use of the Internet.

3.3 Define endpoints. For Aims 2 and 3, HNSCC patients will be assessed at baseline (at study entry) and immediately after viewing the web-based program. Healthcare professionals will provide feedback only once, after viewing the web-based program.

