7.2. Aims 2 and 3 – Evaluation of Web-Based Program

7.2.a. Baseline Assessment

Demographic variables including age, gender, race and ethnicity, education, income and occupation, and marital status will be assessed. In addition, participants' prior use of the Internet (both general use and for seeking health information) will be measured.

Disease characteristics including tumor site, disease stage, grade of differentiation, and Karnofsky performance status (KPS)⁷¹ will be obtained by research staff from medical chart review. Treatment variables including length of treatment and dosage will be obtained by research staff from medical chart review.

To obtain preliminary effect sizes for future trials (**Exploratory Aim 3**), we will also assess quality of life, psychosocial functioning, and self-efficacy. Quality of life (QOL) and Head and Neck-specific QOL will be measured using the EORTC Quality of Life Questionnaire (EORTC QLQ-C30⁷²) and the Head and Neck Module (EORTC-H&N35⁷³), respectively. The EORTC QLQ-C30 is a validated cancer-specific self-report questionnaire^{25,26,74-76} that consists of a global quality-of-life scale, 5 functional scales, and 9 symptoms scales. The EORTC QLQ-H&N35 is designed to be used together with the QLQ-C30 and has good reliability and validity among patients with head and neck cancer^{77,78}. Psychosocial functioning (namely, general and cancer-specific distress) will be measured using the Brief Symptom Inventory-18 (BSI-18⁷⁹), an 18-item instrument that has been used extensively with medical populations⁸⁰ and in our prior studies. The BSI-18 is highly reliable and valid and yields a composite score (Global Severity Index) and three subscale scores: somatization, depression, and anxiety. Cancer-specific distress will be measured using the Impact of Events Scale (IES), which is a well-validated self-report measure of avoidant and intrusive ideation⁵³. Self-efficacy for coping with cancer-related stressors and activities will be assessed using the brief version of the Cancer Behavior Inventory (CBI-B)⁸¹, which is a 14-item shortened version of the original CBI.

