A subset of psychosocial measures (general and cancer-specific distress, self-efficacy) will be administered again after patients have viewed the website to obtain preliminary data on intervention impact. Given that patients will have only had the opportunity to review the web-based program (but not engage in any practice), changes in functional status are not anticipated, and therefore, the QOL measures will not be re-assessed.

7.2.b. Patient Evaluation of the Web-based Program

Patients will evaluate the web-based program in the following four areas: (1) Satisfaction with the web-based program; (2) Identification of material that patients liked and disliked; (3) Plans to use the web-based program and/or recommend it to others; and (4) Overall evaluation of program content and format. Sample assessment questions are: a) Overall, how informative was this web site? (rated on a scale from 1-Not informative to 5-Extremely informative); b) How useful was the section on treatment side effects? (rated on a scale from 1-Not useful to 5-Extremely useful); c) How useful was the section on changes in swallowing? (similar questions to be asked for each topic unit, e.g., changes in speech, coping with cancer); d) Were the physical therapy videos useful?; e) If you could access this web-based program at home, how easily would you be able to use this on your own?; f) Overall, I would rate this program... (from 1 – “Poor” to 5 – “Excellent”); g) Overall, I would be likely to use this web-based program... (1–“Not at all” to 5–“Frequently”); h) Overall, I wish I had access to a web-based program like this now (1–“Strongly disagree” to 5–“Strongly agree”); i) Was there anything that was unclear? If yes, please note which section; j) What other types of

information would you like to have available on this web site?.

7.2.c. Healthcare Provider Evaluation of the Web-based Program

Similarly, 5 healthcare professionals will be asked to provide ratings after viewing the web-based program regarding the usefulness of this program for their patients. Sample items include “The information presented in this program would be useful to my patients” (to be rated from 1 – “Strongly disagree” to 5 - “Strongly agree”) and “I would recommend this program to my patients”.

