8.0 STUDY PARAMETERS

Table 1 presents the measures to be obtained at each assessment time point:

Aims 2 and 3: Measures and Assessment Time Points

Questionnaire Name	# of Items	Time to Complete	Baseline	Follow-up
Demographics	7	5 min	X	
Internet Use	4	5 min	X	
EORTC QOL & H&N35	65	10 min	X	
Brief Symptom Inventory	18	5 min	X	X
Impact of Events Scale	15	5 min	X	X
Cancer Behavior Inventory	14	5 min	X	X
Program Evaluation*	22	10 min		X
Total	143		35 minutes	25 minutes

* Healthcare professionals complete a 7-item program evaluation form only.

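### BSI-18 and IES changes taken immediately after viewing do not estimate a lasting program effect on distress and should not become effect sizes for the future trial

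*Combined protocol and SAP*

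**What the plan says.** Section 3.3 defines the assessment times for Aims 2 and 3: "HNSCC patients will be assessed at baseline (at study entry) and immediately after viewing the web-based program". Section 7.2.a lists what is repeated: "A subset of psychosocial measures (general and cancer-specific distress, self-efficacy) will be administered again after patients have viewed the website". Table 1 agrees. It has one follow-up column, marked for the BSI-18 ("Brief Symptom Inventory 18 5 min X X"), the IES ("Impact of Events Scale 15 5 min X X") and the CBI-B.

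Section 7.2.a describes the BSI-18 as giving a composite and "three subscale scores: somatization, depression, and anxiety", and the IES as "a well-validated self-report measure of avoidant and intrusive ideation". It gives no recall period for either. The patient forms are in Appendix B, which is listed but is not part of the text reviewed.

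Sections 1.0 and 3.0 commit the pre- and post-program data to the calculation of effect sizes in support of a randomized trial. The close of section 2.1.d says that trial will hypothesize better quality of life and psychosocial adjustment. Section 12.2.a plans descriptive means with 95% confidence intervals for Aim 3 and writes out no change-score analysis.

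The quality-of-life forms are not repeated. The reason given begins "Given that patients will have only had the opportunity to review the web-based program (but not engage in any practice), changes in functional status are" and concludes that no such change is expected.

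**The concern.** Somatization, depression, anxiety, intrusion and avoidance are symptoms that a patient experiences over time. At the only follow-up, the patient has just finished viewing. What the second score can show then depends on the form's instructions:

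- **Past-period wording.** The patient reports on days that almost all came before the program. A lasting benefit would be largely missed.
- **Present-moment wording.** The patient reports how the session left them feeling. That is a real quantity, but it is not the sustained distress outcome that a later trial of adjustment would target.

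In neither case is the pre/post change an estimate of lasting program impact on distress, yet Aim 3 would turn it into an effect size. The practical risk is that a value near zero is read as evidence that the program does not affect distress, or that a value of either sign is used to size the next trial.

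The CBI-B is different. It measures confidence in coping, which viewing alone could plausibly shift and which section 2.1.c treats as the route by which the program works.

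**Working it through.** **1. The plan's own precision figure.** Section 12.2.a states a 95% confidence interval of ±0.29 SD around a mean with 45 participants. Check: 1.96/√45 = 0.292, so it reproduces (0.300 with the t quantile). This figure does not depend on when the forms are given.

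**2. Inputs for the timing check.**
- From the documents: follow-up immediately after viewing (3.3); n = 45, and up to 75 patients (12.2.a, 3.0).
- Assumed, because the documents do not give them: look-back W of 1, 3 or 7 days; viewing time h of 0.5 to 2 hours; a lasting true effect of 0.5 SD; a score that averages evenly over the window.

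**3. Share of the window containing any program time** = h / (24 × W). Counting the whole viewing session as program time is generous.

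| Look-back | 0.5 h | 1 h | 2 h | 0.5 SD effect appears as at most |
|---|---|---|---|---|
| 1 day | 2.08% | 4.17% | 8.33% | 0.5 × 0.0833 = 0.042 SD |
| 3 days | 0.69% | 1.39% | 2.78% | 0.5 × 0.0278 = 0.014 SD |
| 7 days | 0.30% | 0.60% | 1.19% | 0.5 × 0.0119 = 0.006 SD |

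**4. Comparison with achievable precision for a change.** With within-patient correlation ρ (assumed), the SD of change is √(2(1 − ρ)) baseline SDs, and the 95% half-width is t × √(2(1 − ρ)) / √n.
- ρ = 0.5, n = 45: 0.300 SD.
- ρ = 0.9, n = 45: 0.134 SD.
- ρ = 0.9, n = 75: 0.103 SD.

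The largest diluted effect in the table, 0.042 SD, is below all three. More patients would not cure this, because it concerns what is measured and not how precisely.

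**5. The role of delay.** This is an illustration only, since the plan specifies no such test. Take a 7-day window, n = 45, a paired t test at two-sided 5%, and a lasting effect of 0.5 SD of change. The recordable effect k days after viewing is 0.5 × k/7.
- 1 hour: 0.003 SD, power about 5%, which equals the type I error.
- 1 day: 0.071 SD, power about 8%.
- 3.5 days: 0.25 SD, power about 37%.
- 7 days: 0.5 SD, power about 91%.

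**6. Present-moment wording.** Steps 3 to 5 do not apply. Section 13.2 foresees worry, discomfort or fatigue during viewing, so the session itself could move the score, possibly upward. That is an immediate reaction and gives no information on whether distress is lower days or weeks later.

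**The case against.** The strongest reply is that the deciding fact, the wording of the forms, cannot be seen, and that the dilution figures rest on stacked assumptions. Even averaging over a window is a strong measurement model: a patient gives one judgement on the day, and current mood or reappraisal can colour it. This stands as a limit on the figures. It does not rescue the planned use, because the conclusion is reached under either wording.

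Several stronger readings are tempting, and the documents do not support them:

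- *The scores are null by construction, or a non-zero change could not come from the program.* Section 13.2 expects that viewing may itself cause worry or discomfort, so a program-related reaction is possible.
- *The protocol contradicts itself by repeating distress but not quality of life.* Its stated reason for omitting quality of life concerns functional status without practice. Section 2.1.a links lack of information to uncertainty, anxiety and depression, so a different route for distress is at least arguable. The contrast raises the question but is not an inconsistency.
- *The distress scales are the main Aim 3 data.* Section 3.1 lists psychosocial functioning and self-efficacy without ranking them.
- *The problem is wholly separate from the lack of a control group and the open interval between baseline and viewing (5.2).* With a control arm and a same-day baseline, a difference between arms could be attributed to the program. What would remain is that the difference is an immediate reaction, or a heavily diluted one.

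It is also fair to say that sections 5.3 and 7.2.a say only after viewing, so some home viewers might answer later. Nothing requires this, and section 3.3 is the only place that fixes the timing. Finally, Aim 3 is labelled exploratory and its effect sizes potential, which limits the stakes.

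**Conclusion.** The concern holds in this form: BSI-18 and IES changes taken immediately after viewing do not estimate lasting program impact on distress and should not be used as effect sizes for the future trial. A value near zero would not be evidence of no effect.

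The timing, the repeated forms and the effect-size purpose are all in the documents. The size is conditional: 2.1 to 8.3% of a 1-day window or 0.3 to 1.2% of a 7-day window, and at most 0.042 or 0.006 SD from a true 0.5 SD, under the assumed look-back, viewing time and averaging. The conclusion itself does not need those figures, because present-moment wording leads to the same restriction by another route.

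The point does not extend to the CBI-B, and none of the section 12.2.b success criteria uses the BSI-18 or IES. It is worth fixing because the fix is cheap and the stated use is one the design cannot support.

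**What to change.** In sections 3.0/3.3 and 12.2.a:

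- Limit the immediate post-viewing effect size to the CBI-B.
- Report BSI-18 and IES levels and change after viewing descriptively, with confidence intervals, labelled as short-term reaction. Include any immediate increase in distress, since section 13.2 names that risk.
- State that these changes will not be used as effect sizes for planning, and that a value near zero is not evidence of no effect.
- Allow baseline SDs to inform the future trial. Carry over the within-patient correlation only with caution: overlapping look-back windows could inflate it, and the interval between the two forms is not fixed.

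The cost is wording, with no new patients, forms or visits. The exploratory aim gives up a distress effect size.

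Optionally, if a distress change is wanted, the two forms could be repeated once at least a full look-back period has passed since viewing. Table 1 puts them at 5 + 5 = 10 minutes, but this adds a contact, with the tracking and non-return that come with it. The wording change does not depend on it.
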